7.3 Efficacy Evaluable Population

All subjects who received at least one dose of Debio 1562 and rituximab, and had both baseline and post-baseline evaluable disease assessment (including clinical progressive disease) will be part of the efficacy evaluable population. Reporting in the efficacy evaluable population will be done per the assigned treatment and cohort as per protocol (version 7, Section 10.2).

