10.2 Efficacy Analyses

All summaries will present data by cohort and overall for the efficacy evaluable population. The data summaries of Responses, OS, PFS, and DoR will also be presented by Cohorts and overall for the Efficacy evaluable population. Data summaries for OS and PFS analyses will also be presented for the All treated population.

Subject level data will be provided in listings.

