10.2.1 Multiple Comparisons/Multiplicity

No formal comparison between cohorts will be performed. Therefore, adjustment for multiple comparisons will not be required.

Hypothesis testing will be done only for the primary efficacy endpoint. Therefore, adjustment for multiplicity will not be required.

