10.2.2 Radiologic Tumor Assessment

Tumor response assessment is based on the Lugano classification of response assessment of Hodgkin and non-Hodgkin Lymphoma (Cheson, 2014, see Appendix H).

Radiographic tumor evaluation by computed tomography (CT) or positron-emission tomography (PET)-CT scan of chest, neck, abdomen, and pelvis will be performed within 28 days prior to first dose of study treatment. The anatomical regions to be assessed radiographically post baseline will be determined by individual subject's extent of disease. Repeat assessments will be performed every 6 weeks +/- 1 week, beginning at cycle 1, day 1 and will not shift as a result of delays in study treatment. The same radiographic assessment method used at screening should preferably be used at all subsequent evaluations.

The results from the tumor assessments will be listed for target, non-target, and new lesions including: lesion number, date, site, and method. For target lesions their measurements (LDi, SDi and PPD), sum of product of diameters (SPD), and FDG-PET Deauville score will be provided. Non-target lesions will be assessed and listed as present, not present, or unknown and whether worsened or not. An overall response will be determined by the investigators following the recommendations from the 2014 Lugano classification. If a new tumor is

identified, the date of biopsy, site, size, diagnosis of lymphoma per biopsy, grade, [REDACTED], [REDACTED], and method of assessment (if appropriate) will be listed. As per the 2014 Lugano classification, spleen and liver assessments will also be listed as appropriate.

Subject maximum percent change from baseline for the SPD (MCL, DLBCL, MZL, and FL) and the associated best overall response will be plotted (waterfall plot) for the efficacy evaluable population.

Subjects who have discontinued study treatment for reasons other than PD will be followed by radiographic assessment every 12 weeks (+/- 4 weeks), beginning from the time of the subject's last on-treatment tumor assessment, until documentation of PD, or beginning subsequent anti-cancer therapy. The date of attempted contact, PD status, new anti-cancer therapy status, regimen, and dates will be listed.

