10.2.4.1 Progression Free Survival

PFS is defined as the time (in months) between the date of the first Debio 1562 dose until the earliest of either first occurrence of PD (radiologic or clinical) or death. It is calculated as:

$$(date\ of\ first\ PD/death - date\ of\ first\ Debio\ 1562\ dose + 1) / 30.4375.$$

The following censoring rules will be applied:

1. Subjects who do not experience death or PD, nor initiate a new systemic therapy will be right-censored at the date of their last adequate tumor assessment (i.e. a tumor assessment not showing NE);
2. Subjects having initiated a new systemic therapy before experiencing death or PD will be right-censored at the date of their last adequate tumor assessment prior to initiation of a new systemic therapy;
3. Subjects who experienced death or PD after two or more consecutive missing or inadequate tumor assessments (i.e. $2*6*7 + 2*7 = 98$ days, based on assessments every 6 +/- 1 week) while assessments are done every 6 +/- 1 week will be right-censored at their latest adequate assessment before death or PD;

4. Subjects who experienced death or PD after one or more consecutive missing or inadequate tumor assessments (i.e. $12*7 + 4*7 = 112$ days, based on assessments every 12 +/- 4 week) while assessments are done every 12 +/- 4 week will be right-censored at their latest adequate assessment before death or PD;
5. Subjects without a baseline or post-baseline assessment will be right-censored at the date of first administration of the Debio 1562 unless the subject died within 190 days from the first dose date ($5*(21+3)+21+7+42 = 190$ days, considered as an event at the date of death).

If multiple event and censoring conditions are met for the same subject, then the condition with the earliest date will be selected.

When an analysis cutoff date is implemented, only data occurring on or prior to the cutoff date will be used for analysis and subjects will be censored at the latest adequate assessment prior to cutoff date.

The following sensitivity analyses will be performed:

1. An additional sensitivity analysis for progression-free survival consists of ignoring the 3rd and 4th censoring rules.

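### SAP PFS rules: the earliest-date tie-break can curtail the 190-day death rule in the All treated analysis, and two best-response windows can shut out compliant scans

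*SAP*

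**What the plan says.** **PFS censoring (SAP 10.2.4.1).**

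- Rule 3 concerns "Subjects who experienced death or PD after two or more consecutive missing or inadequate tumor assessments" on the 6-weekly schedule, set at 98 days. It censors at the last adequate assessment before the event.
- Rule 4 does the same on the 12-weekly schedule, with one or more assessments missing and a limit of 112 days.
- Rule 5 censors at first dose a patient who lacks a baseline or post-baseline assessment, "unless the subject died within 190 days from the first dose date". In that case the death is an event on its own date.
- For overlaps, the section states: "If multiple event and censoring conditions are met for the same subject, then the condition with the earliest date will be selected". It makes no exception for rule 5.
- The first sensitivity analysis reads: "An additional sensitivity analysis for progression-free survival consists of ignoring the 3rd and 4th censoring rules".

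**Populations.** Under SAP 7.3 the evaluable patients are those who received both drugs and "had both baseline and post-baseline evaluable disease assessment (including clinical progressive disease) will be part of the efficacy evaluable population". SAP 10.2 adds: "Data summaries for OS and PFS analyses will also be presented for the All treated population".

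**Best-response periods (SAP 10.2.3).** Besides the primary best overall response, best response is summarised up to the first, second and third scheduled assessments. If the preceding scan was done, the second and third periods end 6 weeks + 7 days after that scan. If scans were missed, longer limits apply. The scan schedule itself is fixed (SAP 10.2.2): "Repeat assessments will be performed every 6 weeks +/- 1 week, beginning at cycle 1, day 1 and will not shift as a result" of treatment delays.

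**The concern.** Rule 5 was written for patients who die before any scan can show progression, and its 190-day limit is derived explicitly. A patient with a baseline scan and nothing afterwards can meet both rule 5 (event at death) and rule 3 or 4 (censored at the last adequate assessment). Censoring at baseline always predates the death, so the tie-break always chooses it. A death that the plan means to count leaves the analysis at or before time zero.

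Removing such a patient raises the Kaplan-Meier estimate from the date of death onwards and lowers it slightly before that date. With N patients, k of them event-free and no other censoring, the later estimate moves from k/N to k/(N-1). SAP 10.2.4 reports PFS at 6 months, which is 6 × 30.4375 = 182.6 days. Most of the disputed range lies before that time.

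The best-response windows raise a smaller matter of the same kind. The schedule is anchored to Cycle 1 Day 1 but the window is anchored to the previous scan, so an early first scan can push an on-time second scan out of its window.

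**Working it through.** Days are counted from first dose as day 0.

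**1. The SAP's own limits reproduce.** Rule 3: 2×6×7 + 2×7 = 98. Rule 4: 12×7 + 4×7 = 112. Rule 5: 5×(21+3) + 21 + 7 + 42 = 190. No limit is miscalculated. The issue is which rule prevails.

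**2. PFS for a patient with a baseline scan, no later assessment, and death on day d (1 to 190).** Rule 5 gives an event on day d. If the gap exceeds the rule 3 or rule 4 limit, censoring at baseline also applies and the tie-break selects it. The SAP does not say where the gap starts, so two starts are shown. Day -28 is the earliest baseline scan under SAP 10.2.2.

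| Rule applied | Gap counted from | Death still an event | Death censored | Share of the 190 days |
|---|---|---|---|---|
| 3 (98 days) | first dose | days 1–98 | days 99–190 (92 days) | 92/190 = 48% |
| 3 (98 days) | scan on day -28 | days 1–70 | days 71–190 (120 days) | 120/190 = 63% |
| 4 (112 days) | first dose | days 1–112 | days 113–190 (78 days) | 78/190 = 41% |
| 4 (112 days) | scan on day -28 | days 1–84 | days 85–190 (106 days) | 106/190 = 56% |

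The PFS formula at the censoring date gives (0+1)/30.4375 = 0.03 months for a scan on day 0, and (-28+1)/30.4375 = -0.89 months for a scan on day -28.

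A patient with no assessment at all has no date for rule 3 or 4 to use and keeps the rule 5 event.

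**3. Shares of days are not shares of deaths.** As an illustration only, assume exponential death times with median m, so S(t) = 0.5^(t/m). The fraction of deaths within 190 days that fall on days 99–190 is [S(98) - S(190)] / [1 - S(190)]. This is 9% for m = 30 days and 24% for m = 60 days. The documents give no death-time distribution for these patients.

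**4. Best-response windows.** Compliant scans fall on days 35–49, 77–91 and 119–133.

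- Window 2 closes at scan 1 + 49, on days 84–98. If scan 1 was missed, it closes at 84 + 14 = day 98.
- Window 3 closes at scan 2 + 49, on days 126–140. If scan 2 only was missed, it closes at scan 1 + 98, on days 133–147. If both were missed, it closes at 126 + 21 = day 147.

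A first scan on day 35 closes window 2 on day 84, so a compliant second scan on days 85–91 is excluded. Excluded second-scan days for a first scan on days 35 to 41 are 7+6+5+4+3+2+1 = 28. From day 42 onwards there are none. Of 15×15 = 225 date pairs, 28/225 = 12.4% fall outside. The same count applies to window 3. The missed-scan branches lose none.

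The 12.4% assumes uniform, independent dates. With triangular dates (weights 8 minus the offset in days, independent) it is 5.1%. With uniform dates whose offsets are correlated (Gaussian copula), it is 8.1%, 5.0% and 0.7% at correlations of 0.3, 0.5 and 0.8.

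**The case against.** **Baseline may not be an adequate assessment.** Rule 1 describes an adequate assessment as one not rated NE, and NE is a response category that a baseline scan would not receive. On that reading rules 3 and 4 have no date to censor at, and rule 5 works as written. The negative PFS time also suggests that censoring at baseline was not intended. This has force, and it makes the PFS point conditional. The SAP does not exclude baseline, however, and a baseline scan is literally an assessment not rated NE. Two programmers could reach different event counts.

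**Rule 5 is the specific rule and should prevail.** That is probably the intent, but the tie-break covers any overlap of event and censoring conditions without exception.

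**The reach is small.** This stands. Patients with no post-baseline assessment are outside the efficacy evaluable population, so only All treated PFS is affected. Sensitivity analysis 1 drops rules 3 and 4 and restores these deaths. An affected patient must also outlive the gap with no adequate scan, no clinical progression and no new systemic therapy.

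**The windows serve supplementary tables only.** This also stands. Those tables are cumulative, so a response cut from window 2 can reappear in window 3 and in the primary best overall response.

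A reader might also infer that the end-of-treatment period, which stops at Day 1 of the last cycle + 21 days, is wrong because a compliant third scan can fall later. The documents do not support that. The cut-off matches the treatment duration defined in SAP 10.4, and it is a different summary from best response to the third assessment.

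**Conclusion.** Both rules are wrong as written, and both effects are minor.

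On PFS, if baseline counts as an adequate assessment, rule 5 is curtailed to deaths up to day 98 (or day 70) under rule 3, or day 112 (or day 84) under rule 4. A reader might infer that the 190-day exception is cancelled outright. It is not: earlier deaths remain events, and so do deaths up to day 190 in patients with no assessment at all. A reader might also take 48% or 63% as the share of deaths lost. These are shares of calendar days, and the number of affected deaths cannot be derived from the documents.

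On best response, compliant second and third scans can be excluded after an early preceding scan. The 12.4% rests on assumed scan dates and falls below 1% under strong correlation.

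Neither fault supports a claim about the tested endpoint. SAP 10.2.1 states: "Hypothesis testing will be done only for the primary efficacy endpoint". That endpoint is ORR, and the primary best overall response does not use these windows.

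**What to change.** **PFS (SAP 10.2.4.1).** Add a sentence: for a death within 190 days of first dose with no post-baseline assessment, rule 5 takes precedence over rules 3 and 4, and the earliest-date tie-break does not apply between them. Leave rule 2 (new systemic therapy) unchanged. All deaths on days 1–190 that rule 3 or 4 would otherwise have censored then remain events, wherever the gap is counted from.

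**Best response (SAP 10.2.3).** Close window 2 at the later of day 91 after first dose and the present cut-off. Close window 3 at the later of day 133 and the present cut-off. Keep the missed-scan branches. No compliant second or third scan is then lost. The latest closings, days 98 and 147, still precede the opening of the next scan windows at 126 - 7 = day 119 and 168 - 7 = day 161.

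The cost is SAP wording and programming. No new data are needed.

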- the patient must terminate his/her ongoing weekly administration cycle before switching to the Q3W regimen. For instance, if the patient received his/her first weekly administration of 0.4 mg/kg (D1), he/she should continue to receive weekly treatment until the end of that cycle. Only then, the patient can start the Q3W dosing regimen (0.7 mg/kg);
- patients who switch should continue to receive the Q3W regimen for the remainder of the study.

This will reduce the number of visits to the hospital. Therefore, reducing the exposure of patients to a potential risk of contamination, while ensuring adequate treatment. The measure taken will also reduce the burden at the trial sites during the pandemic.

**Treatment and study duration:** Patients will receive study treatment for six 21-day cycles, or until they develop unacceptable toxicity, withdraw consent, or the Sponsor terminates the study. Permission to prolong the study treatment could be exceptionally granted by Study Sponsor if patients are deriving benefit from the study treatment and after complete presentation of the individual case by the Study Investigator, particularly the medical justification for extending the treatment and the re-assessment of the risk/benefit balance. The Sponsor's decision will consider the availability of the Investigational Medicinal Product (IMP) at the time of the request. A report of the discussions with the Sponsor must be filed in the source documentation.

Patients who display intolerance to the combination regimen may be eligible to continue treatment with single agent Debio 1562.

Patients who discontinue the study treatment for reasons other than PD (including treatment completion) will be followed by radiographic scan, every 12 weeks ( $\pm$  4 weeks) from the time of their last on-study tumor assessment until PD, start of any new anti-cancer therapy, or death.

For patients who are exceptionally granted continued study treatment after completion of 6 cycles, repeat radiographic tumor response assessments can be performed as per local institutional care practice. Ideally, repeat assessments should continue at 6-week ( $\pm$  1 week) intervals and should not be longer than 12-weeks ( $\pm$  4 weeks). Periodic tumor assessment will be conducted using the same imaging modality of prior cycles of treatment until PD, start of any new anti-cancer therapy, or death.

[figure not shown]

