### **5.10.1. Discontinuation from Study Treatment**

Patients may be withdrawn from study treatment at any time at their own request, or they may be withdrawn at the discretion of the Investigator or Sponsor for safety or non-compliance to the protocol.

Reasons for permanent discontinuation of both study drugs may include the following:

- Radiological PD
- Clinical progression
- Withdrawal of consent to study treatment, but agrees to the protocol-defined follow up

- AE
- Investigator decision
- Study terminated by Sponsor
- Major protocol deviation or non-compliance
- Patient becomes pregnant
- Death
- Other

Depending on the disease state and the tumor response, patients who permanently discontinue study treatment will enter into the response and survival follow-up portion of the study: patients who had discontinued study treatment due to PD will be followed-up for survival every 12 weeks ( $\pm$  4 weeks) for up to one year from the last patient's first dose (Cycle 1 Day 1); Patients who discontinued the treatment for reasons other than PD (including treatment completion) will be followed by radiographic assessment every 12 weeks ( $\pm$  4 weeks) from the time of the patient's last on-study tumor assessment until documentation of PD or beginning of subsequent anti-cancer therapy (regimen and start date to be recorded in the EDC). After the response follow-up, patients will enter into the survival follow-up. Patients will not be required to visit the clinic for survival follow-up.

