### **8.14. Radiologic Imaging and Tumor Response Assessment**

Tumor response assessment will be based on the 5-point scale per the Lugano classification of response assessments of Hodgkin and NHL ([Cheson 2014](#)).

Radiographic tumor evaluation by computed tomography (CT) or positron-emission tomography (PET)-CT scan of chest, neck, abdomen, and pelvis will be performed within 28 days prior to first dose of study treatment. The anatomical regions to be assessed radiographically post baseline will be determined individually by extent of disease. Though less preferred, a MRI is acceptable. Patients with FDG-avid disease will be followed by [ $^{18}\text{F}$ ]-FDG-PET scan. Repeat assessments will be performed every 6 weeks  $\pm$  1 week, beginning at Cycle 1, Day 1 and will not shift as a result of delays in study treatment.

Whenever possible, the same radiographic scan assessment used at screening (e.g., PET-CT) should be used at all subsequent radiographic evaluations.

**Response Follow-up:** Patients who have discontinued study treatment for reasons other than PD will be followed by radiographic assessment every 12 weeks ( $\pm$  4 weeks), beginning from the time of the patient's last on-study tumor assessment, until documentation of PD, or beginning subsequent anti-cancer therapy or death.

For patients who are exceptionally granted continued study treatment after completion of 6 cycles, repeat radiographic tumor response assessments can be performed as per local institutional care practice. Ideally, repeat assessments should continue at 6-week ( $\pm$  1 week) intervals and should not be longer than 12-weeks ( $\pm$  4 weeks). Periodic tumor assessment will be conducted using the same imaging modality of prior cycles of treatment until PD, start of any new anti-cancer therapy, or death.

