2. For progression-free survival, subjects who do not experience disease progression or death or who initiate anti-cancer therapy other than for a transplant or CAR-T will be right-censored at the date of their last adequate tumor assessment using the same rules as above. Hence, data collected after a transplant therapy or CAR-T until PD, death or last adequate tumor assessment - whichever occurs first will be included in the PFS derivation.
3. An additional analysis will be done by censoring the Cohort B subjects who have switched to Q3W regimen at their last assessment date while they were still in QW regimen
4. An additional analysis will be done by censoring the subjects who died due to Covid-19 at their death date, if they haven't progressed yet.

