10.2.4.2 Duration of Response

Duration of Response is defined as the time between the earliest date of CR or PR response and the date of the first occurrence of PD or death and calculated as:

$(date\ of\ first\ PD/death - date\ of\ first\ CR/PR + 1) / 30.4375.$

Censoring rules for PFS will be applied to DoR. The DoR will be estimated for all evaluable subjects who achieve an objective response of PR or CR.

The sensitivity analyses for PFS will also be reproduced for DoR.

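### The PFS and DoR sensitivity analysis meant to include follow-up after transplant or CAR-T does so one-sidedly: without off-protocol scans, event-free patients gain no time and, on the natural reading, late events are censored back to the pre-transplant scan

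*SAP*

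**What the plan says.** **What the analysis is for.** Main PFS rule 2 (SAP 10.2.4.1) censors a patient who starts new systemic therapy at the last adequate scan before it. Sensitivity analysis 2 lifts this for transplant and CAR-T, so that "data collected after a transplant therapy or CAR-T until PD, death or last adequate tumor assessment" counts. It refers back to the rules listed before it for censoring. SAP 10.2.4.2 adds: "The sensitivity analyses for PFS will also be reproduced for DoR".

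**What the censoring rules do.** Rule 4 covers "Subjects who experienced death or PD after one or more consecutive missing or inadequate tumor assessments" on the 12-weekly schedule and censors at the latest adequate scan, with a window of 112 days. Rule 3 does the same on the 6-weekly schedule, with 98 days. Where several conditions are met, the earliest date is taken. Only sensitivity analysis 1 says that rules 3 and 4 are ignored.

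**What is collected.** Protocol 8.14 runs response imaging "until documentation of PD, or beginning subsequent anti-cancer therapy or death". Protocol 5.10.1 has the same stop ("until documentation of PD or beginning of subsequent anti-cancer therapy"), as do the Protocol Synopsis ("until PD, start of any new anti-cancer therapy, or death"), the footnotes to Protocol Appendices A to C, and SAP 10.2.2. None makes an exception for transplant or CAR-T. Protocol 5.10.1 continues: "After the response follow-up, patients will enter into the survival follow-up". That phase requires no clinic visit.

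**The concern.** The analysis exists to show whether censoring at transplant or CAR-T distorts PFS and DoR. That requires two kinds of information after the procedure: failures, and time spent free of progression. The protocol stops requiring the scans that would supply the second kind, and the analysis still dates event-free follow-up by scans. A patient in lasting remission after transplant may therefore be handled identically in both analyses.

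The risk is misreading. If few patients can change, the two curves will lie close together, and this could be reported as robustness to transplant censoring when much of the agreement follows from the rules. For DoR, the patients affected are responders who go on to one of these procedures.

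**Working it through.** **1. The plan's own windows reproduce** (SAP 10.2.4.1).
- Rule 3: 2×6×7 + 2×7 = 98 days.
- Rule 4: 12×7 + 4×7 = 112 days.

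**2. The rules applied to example patients.** Assumed dates: last adequate scan on study day 126, transplant on day 147, 12-weekly schedule, no scan entered afterwards. PFS in months is study day / 30.4375. The rule 4 cut is 126 + 112 = day 238.

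| Course after transplant | Main analysis | Sensitivity 2, rules 3/4 kept | Sensitivity 2, rules 3/4 lapse |
|---|---|---|---|
| PD or death day 200 | censored 4.14 | event 6.57 | event 6.57 |
| PD or death day 239 | censored 4.14 | censored 4.14 | event 7.85 |
| PD or death day 400 | censored 4.14 | censored 4.14 | event 13.14 |
| Alive, no PD | censored 4.14 | censored 4.14 | censored 4.14 |

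On the 6-weekly schedule with the last scan on day 42, the cut is day 140. Death on day 120 is an event; death on day 141 is censored at day 42.

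The last row is the same under every reading: event-free time gained is zero. Letting rules 3 and 4 lapse lengthens follow-up only in the rows where the patient fails.

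**3. How many events fall inside the window if rules 3/4 are kept.** The documents give no post-transplant rate, so this is a range under an assumed exponential time from transplant to PD or death with median m months. With window W and gap g from last scan to transplant, the usable time is L = W − g.
- Patients with an event inside the window: p = 1 − exp(−ln 2 × L / (30.4375 m)).
- Patients with an event in the first year: q = 1 − exp(−ln 2 × 365.25 / (30.4375 m)).
- Share of first-year events kept: p / q.

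For W = 112 and an assumed g = 28, L = 84:

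| m (months) | p | Patients unchanged, 1 − p | p / q |
|---|---|---|---|
| 3 | 47% | 53% | 50% |
| 6 | 27% | 73% | 36% |
| 12 | 15% | 85% | 30% |
| 24 | 8% | 92% | 26% |

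Over gaps of 0 to 84 days and the same medians, p / q runs from 61% down to 9% under the 112-day rule, and from 56% down to about 5% under the 98-day rule. These figures assume that every PD after transplant is recorded, so they are generous to the analysis.

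**The case against.** **Scans are not forbidden.** The protocol ends the requirement to scan; it does not bar recording later scans. SAP 8.4 uses unscheduled assessments for endpoints not tied to a timepoint, which covers PFS and DoR. A local scan entered after transplant would extend event-free time and restart the 98- or 112-day count. This stands. A reader might infer that the analysis can include nothing after transplant; the documents do not support that, both for this reason and because PD or death inside the window does become an event.

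**Retention of rules 3 and 4 is not explicit.** The back-reference in sensitivity analysis 2 grammatically attaches to patients being censored. Rules 3 and 4 are also limited to periods when scans run on a schedule, and the analysis states an intention to include data up to PD or death. This stands as an ambiguity. Retention remains the natural reading, since only sensitivity analysis 1 drops the rules. The alternative does not rescue the analysis: it extends follow-up only for failures.

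**The direction of the curve is not fixed.** A reader might infer that the sensitivity curve can only equal or fall below the main curve. That is false. Take ten patients at risk. A is transplanted and B progresses on day 150. With A censored on day 127, the curve after day 150 is 8/9 = 0.889. With A an event on day 200, it is 9/10 = 0.900 until day 200, then 0.800. What is one-sided is which data enter, not the ordering of the curves at every time.

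**Other analyses and limited stakes.** Sensitivity analysis 1 drops rules 3 and 4 but keeps rule 2, so these patients are still censored at the new therapy. Overall survival follows deaths but says nothing about progression. These are secondary endpoints, hypothesis testing is confined to the primary efficacy endpoint (SAP 10.2.1), and excluding patients eligible for a first autologous transplant in Parts 2 and 3 plausibly limits the numbers. All of this limits the importance of the point but does not make the analysis answer its question.

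**Conclusion.** The point holds in a qualified form. Without off-protocol scans, event-free patients gain no follow-up over the main analysis. With rules 3 and 4 kept, PD or death beyond 112 days (98 on the 6-weekly schedule) from the last adequate scan is also lost. With them lapsed, only failing patients are followed longer. Neither reading tests whether censoring at transplant or CAR-T matters, and two programmers could derive different results from the same text.

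Under the assumptions above (rules kept, 112-day window, 28-day gap, median 3 to 24 months, no later scans), 53% to 92% of transplant or CAR-T patients have the same PFS in both analyses, and 50% to 74% of their first-year events are censored back. A reader counting deaths alone might infer that nearly all such patients are unchanged, but SAP 10.2.4.1 also counts radiologic and clinical PD. The effect on the cohort's PFS or DoR cannot be computed, because the number of these patients and whether later scans were entered are not given.

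This should be corrected, but it does not touch the primary endpoints.

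**What to change.** In sensitivity analysis 2 and its DoR copy, before database lock, make two changes together:

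1. State that rules 3 and 4 do not apply after transplant or CAR-T, so PD or death after the procedure is an event on its date.
2. Censor event-free patients at the last scan or contact at which they were documented progression-free, including unscheduled scans.

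The first change alone would increase the one-sidedness. Both are confined to transplant and CAR-T patients, so any difference from the main analysis still comes only from them.

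First confirm that PD status was collected after the new therapy. SAP 10.2.2 lists PD status from contacts, but in its paragraph on response follow-up, which ends at new therapy; the survival listing in SAP 10.2.4.4 names survival status and new therapy, not PD. If it was not collected, do not present the result as post-transplant PFS. Label it as counting only deaths after the procedure, with survivors censored when last known alive.

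The cost is SAP wording and one changed derivation. PD dates from contacts or local care are less precise than those from protocol scans, but only in a sensitivity analysis.

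### The QW-to-Q3W switch-censoring rule suits PFS, but copied unchanged it can place the DoR censoring date before the DoR origin, and in OS it discards a little known survival

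*SAP*

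**What the plan says.** Amendment 6 let Cohort B patients move from weekly to three-weekly dosing during the pandemic, but only after finishing the current 21-day cycle (Protocol Section 5.7.4.1). Protocol Section 10 leaves the matching sensitivity analysis to the SAP.

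The SAP uses one sentence for this throughout. PFS sensitivity analysis 3 (Section 10.2.4.1) consists of "censoring the Cohort B subjects who have switched to Q3W regimen at their last assessment date while they were still in QW regimen". The same words appear for ORR in Section 10.2.3 and for OS in Section 10.2.4.4.

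For DoR, Section 10.2.4.2 says only: "The sensitivity analyses for PFS will also be reproduced for DoR". That section defines DoR as the "time between the earliest date of CR or PR response and the date of the first occurrence of PD or death" and sets its population: "The DoR will be estimated for all evaluable subjects who achieve an objective response of PR or CR". Where several event or censoring conditions apply, the PFS rules, which also govern DoR, say "then the condition with the earliest date will be selected".

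In the main OS analysis, patients who have not died are censored when last known to be alive.

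**The concern.** A censoring date makes sense only if it falls on or after the time origin. PFS and OS start at the first Debio 1562 dose, so a date during QW treatment is safe. DoR starts at the first response, which can come after the switch. The DoR analysis set is not limited to responses reached on QW, so the rule can produce a censoring date earlier than the start date.

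The programmer would then have to choose, with the data in hand, between three treatments of that record. Dropping it or setting it to zero leaves the Kaplan-Meier curve the same but changes the number of responders, the proportion censored and the minimum. Using the follow-up after the switch changes the curve and defeats the purpose of the analysis. With so few switchers, one record is a large share of what is being tested. The same patient would also be a responder for DoR but not in the matching ORR sensitivity analysis.

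The OS issue is smaller. The natural cut-off for survival on QW is the switch itself, when the patient attends for dosing and is known to be alive. An earlier assessment date gives up known survival for no gain.

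**Working it through.** **Inputs.**
- Month length: 365.25/12 = 30.4375 days, which reproduces SAP Section 9.1.
- Scans every 6 weeks ± 1 week from Cycle 1 Day 1 (SAP Section 10.2.2): nominally 42, 84 and 126 days after first dose.
- Switch at the end of a 21-day cycle: nominally 21, 42, 63, 84 or 105 days after first dose.
- Possible switchers: three patients on QW treatment on 14 April 2020, with enrolment complete (Protocol Section 1.9).
- The scan and switch days are nominal schedule days, not trial data.

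**DoR.** The formula is (end date − date of first CR/PR + 1)/30.4375.
- Last QW scan day 42 (stable disease), switch at day 42 or 63, first PR day 84: (42 − 84 + 1)/30.4375 = −41/30.4375 = −1.35 months.
- Same patient, first PR day 126: (42 − 126 + 1)/30.4375 = −83/30.4375 = −2.73 months.
- With the ± 1 week window, consecutive scans lie 28 to 56 days apart. First response at the next scan then gives (−28 + 1)/30.4375 = −0.89 to (−56 + 1)/30.4375 = −1.81 months.
- Switch after Cycle 1: there is no on-treatment QW scan, so the rule supplies no tumour-assessment date at all.

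The earliest-date rule does not help, because it selects the early censoring date. For a patient whose first response is at the last QW scan the formula works: (42 − 42 + 1)/30.4375 = 0.03 months. The problem is confined to responses that come after the switch.

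**OS.** The formula is (end date − first dose date + 1)/30.4375, reading the assessment as a scan.
- Switch at day 63, last QW scan day 42: (42 + 1)/30.4375 = 1.41 months, against (63 + 1)/30.4375 = 2.10 months at the first Q3W dose. The loss is 63 − 42 = 21 days.
- Switch at day 105, last QW scan day 84: 2.79 against 3.48 months, again 21 days.
- Switch at day 42 or 84: scan and switch coincide, and nothing is lost.

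If the assessment is instead read as a clinic visit, the last one on QW is Day 15, which is 14 days into the cycle. The next cycle starts 21 days in, so the loss is 21 − 14 = 7 days. Either way it is nominally 0 to 21 days per switcher.

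**The case against.** The strongest reply concerns DoR. ORR is binary, so the same sentence in Section 10.2.3 can only mean ignoring assessments after the switch. Carried to DoR in that sense, a patient without a response at the last QW scan is not a responder and has no duration. The negative value arises only by taking the response date from after the cut and the censoring date from the cut. This is a sensible reading and probably the intended one. But Section 10.2.4.2 does not state it: its population is every evaluable responder, and the carry-over has no qualification. Writing the intended reading down is exactly the fix proposed here.

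Three stronger readings are tempting, and the documents do not support them.
- A reader might infer that the PFS switch rule itself is wrong. It is not: PFS censoring rules 1 and 2 also go back to the last adequate scan.
- A reader might infer that OS could turn negative for a patient who switches after Cycle 1, because the only scan is the screening one. That scan was not taken while the patient was on QW, so it does not meet the rule's own condition. Section 10.2.4.4 does not say that the assessment must be a scan.
- A reader might infer an error in PFS sensitivity analysis 4, "censoring the subjects who died due to Covid-19 at their death date, if they haven't progressed yet". Rule 1 would go back to the last scan, so this is an arguable departure. But it keeps the time the main analysis would use and changes only the event status, and progression in this SAP includes clinical progression. It is a defensible choice.

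**Conclusion.** The point holds for the carry-over to DoR and, to a small degree, to OS. As written, the DoR switch analysis has no usable time for a Cohort B patient whose first response follows the switch: -1.35 months in the nominal case, -2.73 months if the response comes one scan later. Its responder set also need not match that of the ORR sensitivity analysis. In OS the rule gives up nominally 0 to 21 days of known survival on QW per switcher, against the SAP's own last-known-alive principle. Removing survival time after the switch is the purpose of that analysis and is not counted as a loss.

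At most three patients are involved. The documents do not show that any of them first responded after switching, or when they switched. The main analyses and the primary endpoint are untouched. This is a worthwhile clarification of sensitivity analyses on secondary endpoints, not a threat to the trial's conclusions.

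**What to change.** Add two sentences to the SAP.

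- **Section 10.2.4.2 (DoR):** in the regimen-switch sensitivity analysis, include a Cohort B switcher only if the first CR or PR was recorded on or before the last tumour assessment on QW, and censor event-free switchers at that assessment. This gives the same responders as the ORR sensitivity analysis and removes a patient who switched before any on-treatment QW scan.
- **Section 10.2.4.4 (OS):** in the regimen-switch sensitivity analysis, censor switchers at the date of the first Q3W dose.

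The PFS switch rule and the COVID-19 death analyses can stay as they are. The cost is the two sentences and minor programming. Dosing dates and scan dates are already collected, so no new data are needed.
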